11.2.4 Safety Analyses

Safety Analysis specified in this SAP will be included in the interim analysis except summary of other baseline characteristics listed in Section 7.1:

The following safety results will be summarized in the interim analysis:

- Overview of TEAEs (treatment emergent adverse events).
- TEAEs by SOC (system organ class) and PT (preferred term).
- Treatment-emergent SAEs (serious adverse events) by SOC and PT.
- TEAEs leading to study drug discontinuation by SOC and PT.
- TEAEs by SOC and PT and maximum relationship to study drug.
- TEAEs by SOC and PT and maximum toxicity grade.
- AESIs (adverse events of special interest) by SOC and PT.
- Listing of Pre-treatment SAEs.
- Listing of SAEs.
- Listings of AESIs.
- Listing of Aes leading to death.
- Listing of Aes leading to study drug discontinuation.

- Analysis of mean change from baseline in laboratory and vital sign variables.
- Summary of potentially clinically significant laboratory and vital sign variables.
- Listings of potentially clinically significant laboratory and vital sign variables.
- Shift tables for laboratory and vital sign variables.

12.0 Overall Type-I Error Control

All tests will be performed at two-sided statistical significance level of $\alpha=0.1$. No multiplicity adjustment will be conducted.

13.0 Version History

Table 4. SAP Version History Summary

Version	Date	Summary
1.0	12 Apr 2019	Original version
2.0	24 July 2021	
 • Revise the SAP per the latest SAP template and to maintain consistency with the most recent protocol. • Add definitions of estimand for primary and secondary endpoints. • Clarified the MI method to handle missing data due to COVID-19 and other reasons. • Update Hy's Law rules to be consistent with the most recent Upadacitinib PSSAP. • Add sections to include the planned interim analysis.
3.0	17 Dec 2021	
 • Update SAP language to be consistent with Protocol Amendment Version 7. • Add one efficacy endpoint in Section 3.3 • Update subgroup analysis for primary endpoint in Section 8.7. • Clarify how efficacy analysis and safety analysis will be performed for discontinued treatment groups and continued treatment groups if the study is partially terminated after the planned interim analysis,
4.0	26 July 2022	
 • Update AESI searching criteria to be consistent with the most recent Upadacitinib PSSAP. • Add additional efficacy endpoints for exploratory purpose in Section 3.3.

Appendix A. Protocol Deviations

The number and percentage of subjects who reported at least one of the following protocol deviation categories will be provided.

- Subject entered into the study even though s/he did not satisfy entry criteria.
- Subject developed withdrawal criteria during the study and was not withdrawn.
- Subject received wrong treatment or incorrect dose of study.
- Subject took prohibited concomitant medication.

Appendix B. Definition of Adverse Events of Special Interest

Adverse Events of Special Interest (AESI) will be identified using the following search criteria:

AESI	Type of MedDRA Query	Broad or Narrow Search	SMQ/CMQ Search Criteria
Serious Infections	CMQ		"Infections" – Subset for SAEs
Opportunistic Infection excluding Tuberculosis and Herpes Zoster	CMQ (code 80000189)		"Opportunistic Infection excluding Tuberculosis and Herpes Zoster"
Herpes Zoster	CMQ (code 80000175)		"Herpes Zoster"
Active Tuberculosis	CMQ (code 80000188)		"Active Tuberculosis"
Possible Malignancy	SMQ	Narrow	"Malignancies"
Malignancy	SMQ	Narrow	"Malignant Tumours"
Non-Melanoma Skin Cancer (NMSC)	SMQ	Narrow	"Skin Malignant Tumours" (SMQ 20000204) removing Melanoma CMQ (code 80000119)
Malignancies excluding NMSC	SMQ	Narrow	"Malignant Tumours" removing NMSC output
Adjudicated GI perforations			Based on adjudicated results (the identification of events to be adjudicated are described in the GI Perforation charter)
Adjudicated cardiovascular events: MACE* Cardiovascular Death Non-fatal Myocardial Infarction Non-fatal Stroke Undetermined/Unknown Cause of Deaths Other Cardiovascular events	Output from CAC		
Anemia	CMQ		"Non-Hemolytic and Non-Aplastic Anemias"

AESI	Type of MedDRA Query	Broad or Narrow Search	SMQ/CMQ Search Criteria
Neutropenia	CMQ		"Hematological Toxicity – Neutropenia"
Lymphopenia	CMQ		"Hematological Toxicity – Lymphopenia"
Renal dysfunction	SMQ	Narrow	"Acute Renal Failure"
Hepatic disorders	SMQ	Narrow	"Drug Related Hepatic Disorders" - Comprehensive Search SMQ
Adjudicated Thrombotic Events: VTE** Deep Vein Thrombosis Pulmonary Embolism Other Venous Thrombosis	Output from CAC		

* MACE: Major Adverse Cardiovascular Events, defined as cardiovascular death, non-fatal myocardial infarction and non-fatal stroke.

** VTE: Venous thromboembolic events, defined as deep vein thrombosis (DVT) and pulmonary embolism (PE) (fatal and non-fatal).

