3.5 Safety

Routine safety evaluations include AE monitoring, physical examinations, vital sign measurements, ECGs, and clinical laboratory testing (hematology, chemistry, and urinalysis) as a measure of safety and tolerability for the entire study duration.

SAEs will be assessed at any dose that results in a death, inpatient hospitalization or prolongation of existing hospitalization, persistent or significant disability/incapacity, or a congenital anomaly.

The following areas of safety interest will be routinely assessed to identify any major safety findings related to immunosuppression or potential risks associated with the individual classes of therapy: serious and/or opportunistic infections, herpes zoster, active TB, malignancies (all types), adjudicated gastrointestinal (GI) perforations, adjudicated cardiovascular events (e.g., major adverse cardiovascular event [MACE]), anemia, neutropenia, lymphopenia, renal dysfunction, hepatic disorders, and adjudicated embolic and thromboembolic events (non-cardiac, non-central nervous system [CNS]) including venous thrombotic events defined as pulmonary embolism and deep vein thrombosis. Specific toxicity management measures will be utilized, as described in Section 6.2, for serious infections, serious GI events, cardiovascular events (MACE), malignancies, ECG abnormalities, and select laboratory

abnormalities. In addition, a 30-day follow-up phone call from the last dose of study drug should occur to determine the status of any ongoing AEs/SAEs, or the occurrence of any new AEs/SAEs.

An unblinded internal DMC will be established to ensure the overall integrity and conduct of the study. DMC reviews will be conducted at regular intervals (see Section 5.10 for more details). Regular systematic reviews of emerging safety data from all clinical studies with elsubrutinib, upadacitinib, and ABBV-599 (elsubrutinib/upadacitinib) combination will be conducted by AbbVie.

An independent external Cardiovascular Adjudication Committee (CAC) will adjudicate all blinded cardiovascular and cerebrovascular events, embolic/thrombotic events, and deaths, as defined in the CAC charter.

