 - Subject's QTcF increases from Baseline ≥ 60 msec, the investigator will evaluate, confirm the value, and treatment should be stopped.
- Subject develops active or latent TB at any time during the study.
- The subject becomes pregnant while on study drug.
- Malignancy, except for localized NMSC or CIS of the cervix.
- Subject is significantly non-compliant with study procedures, including inconsistent study drug dosing, which would put the subject at risk for continued participation in the trial as determined by the Investigator or the AbbVie TA MD.
- Subject develops a GI perforation.
- If a diagnosis of deep vein thrombosis, pulmonary embolus, or non-cardiac, non-neurologic arterial thrombosis is confirmed.

- Subject develops active neuropsychiatric SLE (excluding lupus headache) as defined by the CNS portion of SLEDAI-2K or BILAG.
- Subject develops Class IV lupus nephritis (confirmed by biopsy).

In order to minimize missing data for efficacy and safety assessments, subjects who prematurely discontinue study drug treatment should:

- Continue in the study without receiving study drug
- Have all procedures performed outlined in the Premature Discontinuation (PD) visit, preferably within 2 weeks of study drug discontinuation
- Continue with their regular study visit schedule

No PK or biomarker samples should be collected after the PD visit.

For subjects to be considered lost to follow-up, reasonable attempts must be made to obtain information on the subject's final status. At a minimum, 2 telephone calls must be made and 1 certified letter must be sent and documented in the subject's source documentation.

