Adverse events will be monitored throughout the study to identify any of special interest that may indicate a trend or risk to subjects.

Adverse Events of Special Interest

The following adverse events of special interest (AESI) will be monitored during the study:

- Serious infections
- Opportunistic infections
- Herpes zoster
- Active TB
- Malignancy (all types)
- Adjudicated GI perforations
- Adjudicated cardiovascular events (e.g, MACE)
- Anemia
- Neutropenia
- Lymphopenia
- Renal dysfunction
- Hepatic disorders
- Adjudicated embolic and thrombotic events (non-cardiac, non-CNS) including venous thromboembolic events defined as pulmonary embolism and deep vein thrombosis.

Adverse Event Severity and Relationship to Study Drug

Investigators will rate the severity of each AE according to the National Cancer Institute (NCI) Common Terminology Criteria for Adverse Events (CTCAE) version 5, which can be accessed at: https://ctep.cancer.gov/protocoldevelopment/electronic_applications/docs/ctcae_v5_quick_reference_8.5x11.pdf.

If no specific grading criteria are provided for the reported event, then the event should be as follows:

- Mild (Grade 1): asymptomatic or mild symptoms; clinical or diagnostic observations only; intervention not indicated;
- Moderate (Grade 2): minimal, local or noninvasive intervention indicated; limiting age-appropriate instrumental activities of daily living (ADL) (instrumental ADL refer to preparing meals, shopping for groceries or clothes, using the telephone, managing money, etc.);
- Severe (Grade 3 - 5):
 - Grade 3: severe or medically significant but not immediately life-threatening; hospitalization or prolongation of hospitalization indicated; disabling; limiting self-care ADL (self-care ADL refers to bathing, dressing and undressing, feeding self, using the toilet, taking medications, and not bedridden);

- Grade 4: Life-threatening consequences; urgent intervention indicated;
- Grade 5: Death related to AE.

The investigator will use the following definitions to assess the relationship of the AE to the use of study drug:

Reasonable Possibility – After consideration of factors including timing of the event, biologic plausibility, clinical judgment, and potential alternative causes, there is sufficient evidence (information) to suggest a causal relationship.

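### SAP Appendix B names only venous categories for adjudicated thrombotic events, so the wider embolic and thrombotic AESI defined in the Protocol cannot be counted from it

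*SAP*

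**What the plan says.** SAP Appendix B fixes how each AESI is identified. The adjudicated thrombotic row draws on output from the Cardiovascular Adjudication Committee (CAC). It names VTE and then "Deep Vein Thrombosis Pulmonary Embolism Other Venous Thrombosis". A footnote limits VTE to DVT and PE, whether fatal or not.

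The AESI list in Protocol Section 6.1 is wider: "Adjudicated embolic and thrombotic events (non-cardiac, non-CNS) including venous thromboembolic events defined as pulmonary embolism and deep vein thrombosis". Section 3.5 gives the same scope as an area of safety interest: "adjudicated embolic and thromboembolic events (non-cardiac, non-central nervous system [CNS]) including venous thrombotic events defined as pulmonary embolism and deep vein thrombosis".

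Protocol Section 5.5 includes this among the grounds for stopping study drug: "If a diagnosis of deep vein thrombosis, pulmonary embolus, or non-cardiac, non-neurologic arterial thrombosis is confirmed". Section 6.2 repeats it under thrombosis management.

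Both documents send embolic and thrombotic events to the CAC without limiting them to venous events (Protocol Section 3.5, SAP Section 3.4). Protocol Table 3 provides a dedicated eCRF for embolic and thrombotic events outside the heart and CNS.

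**The concern.** In the Protocol wording, venous events are included in the AESI but do not make up the whole of it. Every label in the SAP row is venous, and the row heading no longer mentions embolic events.

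Appendix B is the operative definition. SAP Section 9.2.2 takes the AESI overview from it. Section 9.2.6 uses it for the summaries through Week 24 and Week 48, the rates per 100 patient-years and the listing. The interim safety outputs in Section 11.2.4 also include AESI summaries and listings.

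The Protocol describes thrombosis in general, not only venous thrombosis, as an increased risk in SLE and a potential risk with JAK inhibitors (Sections 2.2 and 5.2). At stake is whether a reader comparing arms on this AESI sees the category that the Protocol defined or only its venous part.

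**Working it through.** The plan states no figure on this point and no formula applies. The check is a comparison of texts.

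1. **SAP row.** Labels: VTE, DVT, PE, other venous thrombosis. Venous: 4 of 4. Arterial or other non-venous embolic: 0 of 4.

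2. **Protocol AESI (Sections 3.5 and 6.1).** The scope is set by exclusion: adjudicated embolic and thrombotic events that are neither cardiac nor CNS. PE and DVT are given as the included venous part. A peripheral arterial thrombosis or embolism meets the definition by implication, since the AESI list itself does not use the word arterial.

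3. **Protocol discontinuation rule (Sections 5.5 and 6.2).** Three diagnoses are named: DVT, PE, and arterial thrombosis that is neither cardiac nor neurologic. The SAP row has a label for the first two, so 2 of 3. The arterial type is therefore one that the Protocol itself anticipates.

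4. **Where could such an event go in Appendix B?** The only other candidate is the residual line for other cardiovascular events in the separate adjudicated cardiovascular row. The SAP does not define that line. Two outcomes follow:
   - The event fits no line and is absent from the AESI overview, summaries, rates and listings.
   - The event goes into the residual line and is pooled there with other non-MACE cardiovascular events.

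   In neither case do the listed rows add up to the Protocol's category.

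5. **What is still reported.** The SAP outputs outside the AESI set do not depend on Appendix B:
   - TEAEs by SOC and PT, relationship and toxicity grade (Section 9.2.3).
   - Exposure-adjusted rates by SOC and PT (Section 9.2.4).
   - SAEs and AEs leading to discontinuation, tabulated and listed (Sections 9.2.5 and 9.2.9).

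   By step 3, a confirmed arterial case requires study drug to be stopped. If the Protocol is followed and the event is treatment-emergent, it should appear in the discontinuation table and listing. These outputs are organised by MedDRA term, however, not by adjudicated category.

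**The case against.** A reader might infer that arterial thrombotic events are dropped from safety reporting. The documents do not support that. As step 5 shows, the event stays visible in several outputs, and an internal DMC reviews unblinded safety data (Protocol Section 5.10). What is at risk is the AESI category, not detection of the event.

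Nor is it established that such events have no place at all in Appendix B. Protocol Table 3 files the non-cardiac, non-CNS embolic and thrombotic eCRF under cardiovascular AEs, so the CAC charter may send them to the residual cardiovascular line. The charter is not among the documents. This stands as a possibility, but the SAP does not say it, and Protocol Section 6.1 lists cardiovascular events and non-cardiac, non-CNS embolic and thrombotic events as separate AESIs. Pooling them would still hide the Protocol's category.

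The row heading is not itself limited to venous events, and the labels might be only a breakdown beneath it. The table was flattened when the PDF was read, so the hierarchy is uncertain. Even on that reading there is no named line for an arterial event and no stated total.

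Finally, the narrower row may be deliberate. The SAP version history says that Version 4.0 aligned the AESI search criteria with an upadacitinib programme-level plan. That weakens any reading of the row as an oversight. It does not remove the difference from this trial's Protocol.

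**Conclusion.** The point holds in a limited form. The SAP's thrombotic row is narrower than the AESI in Protocol Sections 3.5 and 6.1, and as written that AESI cannot be counted from Appendix B. The effect is confined to AESI summaries, rates and listings. No efficacy endpoint, test or decision rule is touched.

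The size in events cannot be given, because the documents state no rate of arterial events. One event in a planned arm of 65 is 1/65 = 1.5%, but that is true of any single event and says nothing specific about this gap.

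The conclusion assumes that the Appendix B row was read complete; no redaction is marked there and nothing suggests a lost line. It also assumes that no unseen charter or programme-level plan supplies the missing category in the trial's AESI output.

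**What to change.** In SAP Appendix B, under adjudicated thrombotic events:

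- Add a line for adjudicated arterial thrombotic or embolic events outside the heart and CNS.
- Add a total for all adjudicated embolic and thrombotic events outside the heart and CNS, so that the count matches the Protocol AESI.
- Check the CAC charter. If it already places these events in the line for other cardiovascular events, break them out from there, include them in the total, and say so in a footnote.

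The cost is two table lines and the matching AESI output. The eCRF exists and embolic and thrombotic events already go to the CAC, so no new data collection is implied. Whether the CAC output already carries an arterial label has to be confirmed from the charter. The change concerns reporting only and leaves every clinical stopping rule as it is.

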Appendix C. Potentially Clinically Important Criteria for Safety Endpoints

Vital Sign	Category	Criteria for Potential Clinically Important Vital Signs
Systolic blood pressure	Low	Value \leq 90 mmHg and decrease \geq 20 mmHg from Baseline
	High	Value \geq 160 mmHg and increase \geq 20 mmHg from Baseline
Diastolic blood pressure	Low	Value \leq 50 mmHg and decrease \geq 10 mmHg from Baseline
	High	Value \geq 100 mmHg and increase \geq 10 mmHg from Baseline
Weight	High	> 7% increase from baseline
	Low	> 7% decrease from baseline

Appendix D. Attributes of the Estimand for Primary and Secondary Endpoints

	Attributes of the Estimand				
	Population	Endpoint	Treatment	Intercurrent Events	Statistical Summary*
Primary	FAS	Achievement of SRI-4 and steroid dose \leq 10 mg prednisone equivalent once a day (QD) at Week 24.	
Elsubrutinib 60 mg QD and upadacitinib 30 mg QD
 
Elsubrutinib 60 mg QD and upadacitinib 15 mg QD
 
Elsubrutinib 60 mg QD and upadacitinib placebo QD
 
Elsubrutinib placebo QD and upadacitinib 30 mg QD
 
Elsubrutinib placebo QD and upadacitinib placebo QD
	[REDACTED]	Difference in the percentage of subjects achieving SRI-4 and steroid dose \leq 10 mg prednisone equivalent once a day (QD) between groups.
Binary Secondary Endpoint	FAS	
Achievement of SRI-4 at Week 24.
 
Achievement of BILAG-Based Combined Lupus Assessment (BICLA) response at Week 24.
 
Achievement of Lupus Low Disease Activity State (LLDAS) at Week 24.
	
Elsubrutinib 60 mg QD and upadacitinib 30 mg QD
 
Elsubrutinib 60 mg QD and upadacitinib 15 mg QD
 
Elsubrutinib 60 mg QD and upadacitinib placebo QD
 
Elsubrutinib placebo QD and upadacitinib 30 mg QD
 
Elsubrutinib placebo QD and upadacitinib placebo QD
	[REDACTED]	Difference in the percentage of subjects achieving each binary secondary endpoint between groups.

	Attributes of the Estimand				
	Population	Endpoint	Treatment	Intercurrent Events	Statistical Summary*
Continuous Secondary Endpoint	FAS	Steroid burden, assessed as change from Baseline at Week 24.	Elsubrutinib 60 mg QD and upadacitinib 30 mg QD Elsubrutinib 60 mg QD and upadacitinib 15 mg QD Elsubrutinib 60 mg QD and upadacitinib placebo QD Elsubrutinib placebo QD and upadacitinib 30 mg QD Elsubrutinib placebo QD and upadacitinib placebo QD	[REDACTED]	Difference in the mean change from Baseline in Continuous endpoint between groups.
Count Secondary Endpoint		Number of mild, moderate, or severe flares by Safety of Estrogens in Lupus Erythematosus National Assessment (SELENA) SLEDAI Flare Index (SFI), assessed by number and types of flare (mild/moderate, severe, and any) per subject through Week 24 and through Week 48.	Elsubrutinib 60 mg QD and upadacitinib 30 mg QD Elsubrutinib 60 mg QD and upadacitinib 15 mg QD Elsubrutinib 60 mg QD and upadacitinib placebo QD Elsubrutinib placebo QD and upadacitinib 30 mg QD Elsubrutinib placebo QD and upadacitinib placebo QD	[REDACTED]	Ratio in the mean incidence rate of mild, moderate, or severe flares per patient-year between groups.

* Note: In the event the study is partially terminated, terminated groups will be removed from the comparisons above.

Appendix E. Random Seeds

In case of non-convergence, the random seed will be updated by adding 100000 at each attempt until convergence of model happens.

Variables	Random Seed	
	MCMC Procedure	PROC MI
SLEDAI-2K Total Score*	20001	80001
PhGA*	20002	80002
TJC28*	20003	80003
SJC28*	20004	80004
CLASI*	20005	80005
FACIT-F	20006	80006
PtGA	20007	80007
Pain NRS	20008	80008
No new BILAG A or more than 1 new BILAG B disease activity scores	20009	80009

* This only applies when these variables are a component to derive a binary endpoint.
